# 8.5 AE/SAE Reporting Period and Parameter

Safety events are reported from the time of study injection (Day 0) through completion of the study at Day 90. Specifically, solicited AEs to assess local and systemic reactogenicities will be collected at 30 minutes and then daily for 3 days thereafter. If a solicited AE started during the 3 days post-vaccination and continues beyond the 3 days it will continue to be reported as a solicited AE. Unsolicited AEs and SAEs will be reported from Day 0 through the end of the study at Day 90.

# 8.6 Severity of Adverse Events

An investigator who is a qualified physician, will evaluate all adverse experiences as to:

# • Maximum intensity:

- Grade 1: Mild: is awareness of sign or symptom, but easily tolerated;
- Grade 2: Moderate: is discomfort enough to cause interference with usual activity;
- Grade 3: Severe: is incapacitating with inability to work or do usual activity.
- Grade 4: Life threatening: is at immediate risk of death from the reaction as it occurred

Changes in the severity of an AE should be documented to allow an assessment of the duration of the event at each level of intensity to be performed. AEs characterized as intermittent require documentation of onset and duration of each episode.

Grading of reporting temperature are referred to DAIDS Table in Appendix A (II)

0 (no) 1 mild 2 (moderately high) 3 (high)

Other systemic reactions will be assessed in 4 scales as follow:

0 - no	No symptoms
1 -mild	Symptoms, no significant interference with daily activity
2 -moderate	Symptoms, affecting normal daily activity
3 -severe	Symptoms markedly affecting normal daily activity

At the same time, the following systemic symptoms are assessed

- Fatigue/ malaise
- Headache
- Chill
- Arthralgia
- Myalgia
- Nausea
- Vomiting

Women who become pregnant during the study period will be followed for safety until the end of the pregnancy or until the end of the study, whichever is longer.

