## 8.2 Solicited Local and Systemic Adverse Events

Solicited adverse events are pre-specified local and systemic adverse events that are common or known to be associated with vaccination and that are actively monitored as indicators of vaccine reactogenicity. Investigators will not be required to assess causality of solicited adverse events if the onset is during the solicitation periods. If a solicited adverse event progresses beyond the solicited period, it will continue to be reported as a solicited adverse event. If the solicited adverse event occurs after the solicitation period, it will be reported as unsolicited AEs.

For this trial, solicited local and systemic AEs will be assessed by study staff 30 minutes after vaccination then daily for three days by the participants. Participants will be provided with a thermometer, ruler, and diary card to record the presence or absence of solicited AEs, severity of the solicited AE, and use of concomitant medication. The severity of the solicited local and systemic adverse events will be graded using the Toxicity Table for Grading Adverse Events (Appendix A). The specific solicited local and systemic adverse events that will be reported for this trial are:

Solicited local adverse event (at site of injection):

- Erythema/redness—based on size in cm.
- Swelling/induration (hardness at site of injection)—based on size in cm.
- Pain (pain with or without touching the injection site).
- Limitation of arm movement

Systemic Reactions:

- Fever—taken orally by thermometer
- Fatigue/malaise
- Generalized muscle aches
- Joint aches
- Chills
- Nausea
- Headache

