#### **Stopping rules:**

The occurrence of one or more of the following criteria will automatically pause or halt further vaccinations in the study:

- 1. One or more subjects experience a serious adverse event (SAE) that is suspected to be vaccine related.
- 2. One or more subjects experience a grade 4 injection site reaction (such as necrosis or sterile abscess at injection site requiring surgical intervention) that is suspected to be vaccine related.
- 3. Ten or more subjects experience a grade 3 or greater reactogenicity event following vaccination that is suspected to be vaccine related.
- 4. Five or more subjects experience the same grade 3 or more clinical abnormality following vaccination that is expected to be vaccine related

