## II. Definitions of terms used in the Table:

Basic Self-care Functions Adult

Activities such as bathing, dressing, toileting, transfer/movement, continence, and feeding.

LLN Lower limit of normal

Medical Intervention Use of pharmacologic or biologic agent(s) for treatment of an AE

NA Not Applicable

Operative Intervention Surgical OR other invasive mechanical procedures.

ULN Upper limit of normal

Usual Social & Functional Activities Adult

Adaptive tasks and desirable activities, such as going to work, shopping, cooking, use of transportation, pursuing a hobby, etc.

PARAMETER	GRADE 1 MILD	GRADE 2 MODERATE	GRADE 3 SEVERE	GRADE 4 POTENTIALLY	
ESTIMATING SEVERITY GRADE					
SYSTEMIC					
Acute Allergic Reaction	Localized urticaria (wheals) with no medical intervention indicated	Localized urticaria with intervention indicated OR Mild angioedema with no intervention indicated	Generalized Urticaria OR Angioedema with intervention indicated OR Symptoms of mild bronchospasm	Acute anaphylaxis OR Life- threatening bronchospasm OR Laryngeal edema	
Chills	Symptoms causing no or minimal interference with usual social & functional activities	Symptoms causing greater than minimal interference with usual social & functional activities	Symptoms causing inability to perform usual social & functional activities	NA	
Fatigue or Malaise Report only one	Symptoms causing no or minimal interference with usual social & functional activities	Symptoms causing greater than minimal interference with usual social & functional activities	Symptoms causing inability to perform usual social & functional activities	Incapacitating symptoms of fatigue or malaise causing inability to perform basic self- care functions	
Fever (non-axillary	38.0 to < 38.6°C	$\geq$ 38.6 to < 39.3°C	$\geq$ 39.3 to < 40.0°C	≥40.0°C	
Fever (axillary)	37.7 – 38.1°C	38.2 – 38.8°C	38.9 - 40.0°C	>40.0°C	
Nausea	Transient (< 24 hours) or intermittent AND No or minimal interference with oral intake	Persistent nausea resulting in decreased oral intake for 24 to 48 hours	Persistent nausea resulting in minimal oral intake for > 48 hours OR Rehydration indicated (e.g., IV fluids)	Life-threatening consequences (e.g., hypotensive shock)	

HICS COMMITTEE Page 67 Aut 7.9 OF TROPICAL MEDICINE าริตยาลัยม MAHIDOL UNIVERSITY

APPROVED

US

R

ES
PARAMETER	GRADE 1 MILD	GRADE 2 MODERATE	GRADE 3 SEVERE	GRADE 4 POTENTIALL Y LIFE- THREATENIN

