Vomiting	Transient or intermittent AND No or minimal interference with oral intake	Frequent episodes with no or mild dehydration	Persistent vomiting resulting in orthostatic hypotension OR Aggressive rehydration indicated (e.g., IV fluids)	Life-threatening consequences (e.g., hypotensive shock
Headache	Symptoms causing no or minimal interference with usual social & functional activities	Symptoms causing greater than minimal interference with usual social & functional activities	Symptoms causing inability to perform usual social & functional activities	Symptoms causing inability to perform basic self-care functions OR Hospitalization indicated OR Headache with significant impairment of alertness or other neurologic function
INJECTION SITE	REACTIONS			
Injection Site Pain or Tenderness Report only one	Pain or tenderness causing no or minimal limitation of use of limb	Pain or tenderness causing greater than minimal limitation of use of limb	Pain or tenderness causing inability to perform usual social & functional activities	Pain or tenderness causing inability to perform basic self- care function OR Hospitalization indicated
Injection Site Erythema or Redness Report only one > 15 years of age	2.5 to < 5 cm in diameter OR 6.25 to < 25 cm2 surface area AND Symptoms causing no or minimal interference with usual social & functional activities	$\geq$ 5 to < 10 cm in diameter OR $\geq$ 25 to < 100 cm2 surface area OR Symptoms causing greater than minimal interference with usual social & functional activities	$\geq$ 10 cm in diameter OR $\geq$ 100 cm2 surface area OR Ulceration OR Secondary infection OR Phlebitis OR Sterile abscess OR Drainage OR Symptoms causing inability to perform usual social & functional activities	Potentially life- threatening consequences (e.g., abscess, exfoliative dermatitis, necrosis involving dermis or deeper tissue)

Protocol: GPO Tri Fluvac Vaccine Phase II/III\_ Version 3.1 dated 13 Mar 2017

MUINE MAHIDOL UNIVERSITY

E.

PARAMETER GRADE 1 MILD		GRADE 2 MODERATE	GRADE 3 SEVERE	GRADE 4 POTENTIALLY LIFE-
Injection Site Induration or Swelling Report only one > 15 years of age	Same as forSame as forInjection SiteImageErythema orImageRedness, $> 15$ ImageyearsImage	Same as for Injection Site Erythema or Redness, > 15 years of age	Same as for Injection Site Erythema or Redness, > 15 years of Age	Same as for Injection Site Erythema or Redness, > 15 years of age

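### Headache, fatigue/malaise, chills, nausea and vomiting fall under three conflicting severity descriptions, so the counts for stopping rules 3 and 4 and the severity summaries depend on which text is followed

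*Protocol*

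**What the plan says.** Protocol section 8.2 states: "The severity of the solicited local and systemic adverse events will be graded using the Toxicity Table for Grading Adverse Events (Appendix A".

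Section 8.6 holds two further scales.

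- A general intensity scale, graded 1 to 4, for all adverse experiences. Its third level reads "Grade 3: Severe: is incapacitating with inability to work or do usual activity". Its fourth is immediate risk of death.
- A 0-3 scale, introduced by "Other systemic reactions will be assessed in 4 scales as follow", for fatigue/malaise, headache, chill, arthralgia, myalgia, nausea and vomiting. Its top level is "Symptoms markedly affecting normal daily activity". Temperature is handled separately and referred to Appendix A.

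Appendix A sets grade 3 for headache, chills and fatigue/malaise at "Symptoms causing inability to perform usual social & functional activities". For nausea, grade 3 is "Persistent nausea resulting in minimal oral intake for > 48 hours OR Rehydration indicated". For vomiting it turns on orthostatic hypotension or aggressive rehydration. Appendix A also has a grade 4 for fatigue/malaise, headache, nausea and vomiting.

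Under the stopping rules in section 9.3, rule 3 pauses or halts vaccination if "Ten or more subjects experience a grade 3 or greater reactogenicity event following vaccination that is suspected to be vaccine related". Rule 4 does so when five or more subjects have the same clinical abnormality at grade 3 or above. Section 11.4 summarises the safety endpoints by severity. SAP shells TREF 3.10 and 3.12 tabulate systemic reactions as grades 0 to 3 (none, mild, moderate, severe), with p-values and no criteria.

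**The concern.** Three texts claim the same symptoms, and they do not draw the line for grade 3 in the same place. Two graders who both follow the protocol can give one participant different grades. Grade 3 is the unit that rules 3 and 4 count, and those rules act automatically. The severity tables, and the between-group comparisons of maximum grade in the SAP, use the same grades. If staff work from different sections, the database mixes scales and the severe category has no single meaning.

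**Working it through.** The documents state no figure that rests on the grading scale, so there is none to reproduce. The check is a comparison of texts, followed by an illustration.

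**1. Which symptoms are covered twice.** Of the symptoms named for the 0-3 scale, five have a row in the supplied Appendix A: fatigue/malaise, headache, chills, nausea and vomiting. Vomiting is absent from the solicited list in 8.2 but is a solicited event in 11.3.2 and appears in the SAP shells.

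**2. The same episode under each description.**

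| Episode | Appendix A | 8.6, 0-3 scale | 8.6, general 1-4 scale |
|---|---|---|---|
| Headache, fatigue/malaise or chills that markedly limit usual activity but do not prevent it | 2 | 3 | 2 |
| Nausea under 24 hours, oral intake normal, day markedly affected | 1 | 3 | 2 |
| Persistent nausea, minimal intake for more than 48 hours, activity affected but not markedly | 3 | 2 | 2 |
| Fatigue that prevents basic self-care, no immediate risk of death | 4 | 3 (top of scale) | 3 |

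The first two rows move an episode into grade 3 on the 0-3 scale. The third moves one out of it. The fourth shows that an Appendix A grade 4 has no counterpart on the 0-3 scale and no row in TREF 3.10 or 3.12.

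**3. Whether anything resolves the conflict.** Appendix A's instructions send a clinical event back to the protocol only if it is not in the table. These five are in the table. The SAP labels match the 0-3 scale in number and name but carry no definitions.

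**4. Illustration of the effect on the stopping rules.** The documents give no rate of attributed grade 3 reactogenicity under any scale, so the rates *p* below are assumptions. With *n* vaccinated and independent subjects, the number of cases X is Binomial(*n*, *p*).

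Rule 3, P(X ≥ 10):

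| Assumed *p* | *n* = 473 (about half of 945) | *n* = 709 (about three quarters) | *n* = 945 |
|---|---|---|---|
| 0.5% | 0.0002 | 0.004 | 0.023 |
| 1.0% | 0.022 | 0.178 | 0.472 |
| 1.5% | 0.178 | 0.620 | 0.900 |

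Rule 4, P(X ≥ 5) for one symptom at *n* = 945: 0.091 at 0.25%, 0.510 at 0.5%, 0.836 at 0.75%.

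The thresholds as proportions of 945 are 10/945 = 1.06% for rule 3 and 5/945 = 0.53% for rule 4. Near those rates, reclassifying a few participants changes whether a rule is met.

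**The case against.** The best defence is that the documents show an intended split: fever by Appendix A, other systemic reactions on the 0-3 scale. SAP TREF 3.1 and 3.2 give temperature a grade 4 with the Appendix A bands, while TREF 3.10 and 3.12 stop at grade 3. That is fair evidence about the reporting format. It does not settle the definition, because the shells give labels only and section 8.2 still requires Appendix A for solicited systemic events.

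Appendix A also tells the grader to take the higher grade when an event could fall under either of two. That narrows the gap at the border between grades 2 and 3. It does not help where the two texts use different criteria, as for nausea and vomiting.

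The illustration has real limits. Nothing in the documents suggests that the choice of scale triples the grade 3 rate. The nearest figure, severe adverse events in 2/200 vaccine and 1/100 placebo recipients of the earlier trial (section 2.4), covers severe events of any kind and is not a reactogenicity rate. A pause can stop only vaccinations still to be given, so the probabilities at 945 overstate the practical effect. Rules 3 and 4 also require suspected relation to the vaccine, while 8.2 does not require causality assessment for solicited events within the window. That is a separate ambiguity in the same counts.

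A reader might go further and infer any of the following, which the documents do not support.

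- That Appendix A has no criteria for muscle aches, joint aches or limitation of arm movement. The supplied appendix breaks off partway through the injection-site rows, so absence cannot be shown.
- That the 0-3 scale always yields more grade 3 events. For nausea the direction can reverse, as the third episode shows.
- That the ambiguity favours one arm. Assessment is blinded and allocation is random, so nothing points to a differential effect.

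**Conclusion.** The contradiction stands for five symptoms: headache, fatigue/malaise, chills, nausea and vomiting. The protocol gives three descriptions of their severity with different grade 3 criteria, and neither Appendix A's fallback nor the SAP decides between them. It changes what rules 3 and 4 count and what the severity summaries mean.

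The reach is limited. Fever definitions, rules 1 and 2, the proportions with any reaction, the immunogenicity analyses and the sample size are unaffected. No separate severity endpoint exists; severity is a breakdown of the safety endpoints.

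The size of the effect on the chance of a pause is not known. The range from about 2% to 90% for rule 3 rests on assumed rates of 0.5% to 1.5%, full enrolment of 945 and independence between subjects. It shows that the rule is sensitive to the grade 3 rate. It does not estimate what the choice of scale would do.

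**What to change.** Reconcile section 8.2, both scales in section 8.6, Appendix A, the diary card and CRF, stopping rules 3 and 4, and SAP shells TREF 3.10 and 3.12, so that one named scale applies to each solicited reaction. State that rules 3 and 4 count grades on that scale. Print the grade definitions in the SAP shells, with a row for every grade the scale contains. Removing only one of the two scales in 8.6 would leave the other beside Appendix A, so both need attention. Which scale and which cut-points to use is for the sponsor and the DSMB.

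The cost is protocol and SAP wording plus diary and CRF alignment before first vaccination, with no extra visits or staff. For data already collected, the report should state which definitions the graders were given.

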# Adverse Event of Special Interest (AESI)

AESIs are AEs that are considered by the Investigator to be relevant for the monitoring of the safety profile of the investigational vaccine.

\*Potential indicators of oculo-respiratory syndrome (ORS): ORS was first noted to be associated with influenza vaccination during the 2000-2001 influenza immunization campaign in Canada and has since been reported in association with seasonal inactivated influenza vaccination as well. This acute post-vaccination syndrome presents with symptoms such as bilateral conjunctivitis (red eyes), facial swelling and respiratory symptoms (chest tightness, coughing, a sensation of throat closure, difficulty swallowing, hoarseness, wheezing or difficulty breathing). As the symptoms can mimic an allergic reaction, clinical investigators need to be aware of how to distinguish the two conditions as much as possible.

ORS occurring within 7 days after vaccination will be considered as AESI.

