# 4. STUDY DESIGN:

# 4.1 Study Design

This is a phase II/III, non-inferiority double-blinded, randomized, and controlled trial to evaluate the safety and immunogenicity of a single dose the GPO seasonal trivalent inactivated influenza vaccine in male and female adults, ages 18 to 49 years old. Participants will be randomized 2:1 to one of two treatment allocations: 630 to vaccine, 315 to comparator. The study will be double blinded, meaning the study participants, investigators, and the sponsor will be unaware of the treatment allocated to each participant until the clinical trial database is declared final and locked.

All participants will be consented for participation and screened for eligibility through medical history review and physical examination. All volunteers will be checked against the inclusion/exclusion criteria. The screening assessments will be performed up to 30 days prior to the first vaccination. The screening procedures for the study including a medical history, vital signs, and physical examination will be performed. A urine pregnancy test will be done in females on screening day, day 0 prior to vaccination. Female volunteers should avoid pregnancy from the screening visit until at least 60 days after the vaccination by using an effective birth control method. The baseline immune response will be performed on day 0 prior to vaccination. One dose of the investigational vaccine or comparator will be given by intramuscular route (preferred injection site will be the deltoid of the non-dominant arm) after blood collection for immunology assays. Total follow-up period is 90 days for immune response and safety.

There will be 4 clinical visits and 1 phone visit as follows:

- Screening Visit (Day -30 to Day 0) Sign informed consent form, screen for eligibility (medical history review and physical examination)
- Day 0 (can be the same day with screening day): Vaccination day, subjects will remain at the clinic for at least 30 minutes for observation of any reactogenicity after vaccination. A diary card will be provided to the subjects for recording such events for 3 days after vaccination (Day 0-3).
- Day 7 (-3, + 7days): Return the diary card and report any adverse events that occur during the first seven days after immunization. Concomitant medication information will be collected.
- Day 21 (+7 days): Blood specimen collection for immune response, follow-up and report VEI any adverse events.

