## Table 2: Study Schedule and activities

Procedures	Study Day						
		D0	D7	D21	D60	D90	
			(-3, +7)	(+7)	(+14)	(+7)	
	Screening e	Immunization e					
Informed consent	X						
Assessment of entry criteria	Х	(X) f					
Medical history, AE/SAE, Concomitant medication	Х	(X) f	X	Х	Х	Х	
Vital signs	Х	(X) f	Х	Х		Х	
Urine pregnancy test a	Х	(X) f					
Physical examination a	Х	(X)	(X)	(X)		(X)	
Immunization		X					
Diary card b		X (Day 0-3)	X				
Blood for Immune response (HI Assay) (3ml)		X		Х		Х	
Phone call visit c					Х		
Influenza subtype by RT- PCR d			(X)	(X)	(X)	(X)	

Remark

a. Only at screening, the rest when the history suggested [(x) = Optional as indicated by medical history].

b. Diary card will be provided to the subjects for recording reactogenicity for 3 days after vaccination (Day 0-3) and return to review at Day 7.

c. At Day 60, adverse events and influenza-like illness (ILI) will be followed-up by phone call.

d. Determination of influenza subtype by RT-PCR will be done when the ILI is confirmed [(x) = Optional as indicated].

e. Screening day can be the same day as immunization day (D0)

f. Will be done if immunization is not performed on screening day

(x) Optional

ETHICS COMMITTEE FACULTY OF TROPICAL MEDICINE MAHIDOL UNIVERSITY

APPROVED

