# 7.4 Follow-up visits

# 7.4.1 Day 7(-3, +7 days) after Injection: Return the diary card

Subjects will return to the clinic on day 7 to return the diary card and report any adverse events. Subjects will be asked to report any adverse events that occur during the first seven days after immunization. Concomitant medication information will be collected.

At this visit;

- 1. Study staff will confirm participant identity.
- 2. Study staff will review the participant diary card and interim history with the participant and inquire about any new medical events since medical histories were last updated. Any AEs that have occurred and meeting reporting intensity will be recorded in the appropriate section(s) of the CRF. Diary card information will be entered into the CRF.
- 3. The participant will have temperature, pulse rate, and blood pressure recorded. A study clinician will perform a targeted (symptom based) physical examination and record the information on the CRF. Results will be reviewed by study staff and with the participant.
- 4. The participant will be instructed to inform the investigator as soon as possible if he/she experiences an AE requiring medical care and to seek medical care as appropriate. If the participant visits a health care provider, the participant should be sure to inform the health care provider of participation in this study and give the health care provider the contact information for the investigator.
- 5. There are no scheduled visits at week 2 after vaccination. Participants may be asked to come to the study clinic if the investigator follows up on any clinical issue. The participant will inform the study clinic of any medical events and seek medical care as needed. The participant will be instructed to give any health care provide they see the contact information for the investigator. FACULTY OF TROPICAL MEDICINE วิตยาลัยม

MAHIDOL UNIVERSITY

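### Oculo-respiratory syndrome within 7 days is the only named adverse event of special interest, but the plan does not collect or report it in line with that definition

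*Protocol*

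**What the plan says.** The AESI text in Protocol section 8.6 opens with a general statement, "AESIs are AEs that are considered by the Investigator to be relevant for the monitoring of the safety profile of the investigational vaccine", and then names one event, ORS. It says that the syndrome "presents with symptoms such as bilateral conjunctivitis (red eyes), facial swelling and respiratory symptoms", the last of these covering chest tightness, cough, throat closure, difficulty swallowing, hoarseness, wheeze and difficulty breathing. It then sets the time limit: "ORS occurring within 7 days after vaccination will be considered as AESI".

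Section 8.2 introduces a closed list: "The specific solicited local and systemic adverse events that will be reported for this trial are". The local terms are redness, swelling or induration, pain and limited arm movement. The systemic terms are fever, fatigue or malaise, muscle aches, joint aches, chills, nausea and headache. On the diary, Table 2 remark b says: "Diary card will be provided to the subjects for recording reactogenicity for 3 days after vaccination (Day 0-3) and return to review at Day 7".

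The Day 7 visit has a window of -3 to +7 days (sections 4.1 and 7.4.1, Table 2). Section 7.4.1 gives it this task: "Subjects will be asked to report any adverse events that occur during the first seven days after immunization". Section 4.1 says the same. The next scheduled contact is Day 21 (+7 days), where section 7.4.2 has staff ask about medical events since the last visit.

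No table, figure or appendix title in the SAP mentions AESI or ORS.

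**The concern.** An event marked out for special attention, with its own risk window, would normally have questions that cover that window and a planned count by arm. Here three parts of the plan do not meet. The definition runs for seven days and the diary for three. The visit that is meant to cover the remaining days may take place before they have passed. The analysis has no output tied to the definition.

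Section 2.4 describes ORS symptoms as usually mild and quick to resolve without treatment. Such events are easily lost to open questions asked weeks later. Section 7.4.1 also limits CRF entry to AEs that reach a reporting intensity, and I found no definition of that threshold. At stake is how complete the safety record is for the one event that the protocol chose to name.

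**Working it through.** The plan gives no figure for ORS detection, so there is none to reproduce. The check sets the texts side by side and works out the visit timing.

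**1. Signs against solicited terms.** None of the ORS signs in section 8.6 appears in the section 8.2 list. The solicited swelling is at the injection site, not the face. Sections 8.6 and 11.3.2 add vomiting, and SAP TREF 3.11 adds vomiting and rash. None of these is a listed ORS sign.

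**2. Diary against risk window.** The diary ends on Day 3, so Days 4, 5, 6 and 7 (four days) have no diary.

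**3. Visit window.** Earliest visit: 7 - 3 = Day 4. Latest: 7 + 7 = Day 14. A visit on Day 4, 5 or 6 comes before part of the seven days it must cover. After a Day 4 visit, the whole of Days 5-7 is still to come.

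**4. Recall gap after a Day 4 visit.** The Day 21 visit can fall on Day 21 to Day 28.
- Shortest: onset Day 7, asked on Day 21: 21 - 7 = 14 days.
- Longest: onset Day 5, asked on Day 28: 28 - 5 = 23 days.

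With a visit on Day 7 or later the full window is asked about, but Days 4-7 still rest on recall.

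**5. Reporting.** ORS could reach the analysis as an unsolicited AE, collected to Day 90 (section 8.5). TREF 2.3 would show it by preferred term and arm. Appendix 06 would list it with study group and day of onset. Neither applies an ORS case definition or a Day 0-7 limit.

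**6. Expected numbers, for context.** Section 2.4 gives reported ORS rates of 46.6 per 100,000 doses in 2000, falling to 9 in 2003.
- Expected cases in 630 recipients: 630 × 46.6/100,000 = 0.29; 630 × 9/100,000 = 0.06.
- Chance of at least one case, 1 - (1 - p)^630: 25% at the higher rate and 5.5% at the lower.

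Even perfect capture would therefore give no case in about 75% to 94% of such trials at these rates. They are reported rates, so rates under specific questioning could differ.

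**The case against.** The strongest reply is that ORS is already covered by ordinary AE collection, and much of that stands. Staff ask about new medical events at the Day 7 visit (7.4.1) and about AEs since the last visit at Day 21 (7.4.2). Follow-up continues at Day 60 and Day 90. All participants are observed for 30 minutes after injection (8.10). Section 8.9 tells investigators to record a known syndrome rather than its component signs, and section 8.6 alerts them to ORS. A recognised case should therefore be coded as ORS, appear by arm in TREF 2.3, and carry its onset day in Appendix 06. A Day 4 visit also suits the task of returning a diary that ends on Day 3.

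A reader might infer more than the documents support:

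- **That ORS is found only if a participant volunteers it, or is never counted by arm.** Staff do ask, and a recognised case is shown by arm. What is missing is sign-specific prompting and a planned Day 0-7 count.
- **That the diary excludes ORS.** The diary form is not in the documents. Section 7.3 speaks of any local or systemic reaction, and section 10.4 places ORS among systemic reactions, so a free-text entry on the diary days is possible. Only the absence of ORS signs from the named solicited terms is established.
- **That a finding of no ORS would undermine the 0.58% statement in section 11.2.** That sentence concerns vaccine-related SAEs. Table 3 applies the same 0-in-630 limit to study-drug-associated AEs in general. Neither makes a claim about ORS.

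The small expected count is also a fair point: nothing in the documents shows that better capture would change a conclusion.

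**Conclusion.** The point holds as a mismatch between the definition of the AESI and the means of collecting and reporting it. Four days of the window have no diary. A permitted Day 4 visit leaves Days 5-7 to be asked about 14 to 23 days after onset. No output counts ORS over Day 0-7 by arm. Cases that are mild, or not recognised as ORS, may go unrecorded or be scattered over separate preferred terms.

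This is a cheap improvement to safety ascertainment. It does not affect the primary immunogenicity conclusion or the 0.58% statement. The conclusion rests on two assumptions: that the diary follows the section 8.2 list, and that no CRF page outside these documents already prompts for ORS signs. The share of visits that would fall on Days 4-6 is not given, so the number of participants affected cannot be stated.

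**What to change.** 1. Reconcile the Day 7 window in sections 4.1 and 7.4.1 and Table 2 with the visit's seven-day task, so that either the visit or the question about Days 0-7 cannot come before Day 7.
2. Add yes/no prompts for the ORS signs in section 8.6, with onset date, to that visit's CRF.
3. Add one SAP table and one listing of investigator-identified ORS with onset on Day 0-7, by arm, with exact 95% confidence intervals.

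The cost is a few CRF items, one table and one listing, slightly less flexible scheduling of one visit, and some extra minor reports to review. Carrying the diary to Day 7, or counting any single sign as ORS, is a matter of preference and is not needed here. A single-sign composite would also mix ordinary respiratory illness with ORS.

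Where data have already been collected, the by-arm count can be derived from the onset days in Appendix 06, with a statement that ORS signs were not specifically prompted.
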